Mindfulness. The 24-item Five Facet Mindfulness Questionnaire–Short Form (FFMQ-SF) measures 5 factors representing elements of mindfulness: observing, describing, acting with awareness, nonjudging of inner experience, and nonreactivity to inner experience. Higher scores indicate greater mindfulness.

Post-Intervention Interview. We conducted phone interviews with participants after they completed the 8-week intervention period to obtain qualitative feedback regarding the study. Question topics included benefits of using Headspace, things they liked about Headspace or thought could be improved, suggestions for improving the experience of study participants, and experience being in the wait-list control arm.

Data Analyses

Data from patient participants and caregiver participants were analyzed separately. We described baseline distributions between arms. Retention rates were calculated by dividing the number of participants who completed the 8-week surveys by the number of randomized participants. We used the program usage data collected by Headspace to calculate intervention adherence rates—the percent of days within the 8-week intervention period that participants engaged in at least one Headspace session of any length.

To obtain preliminary efficacy results, we performed repeated measures analysis of variance tests comparing change in outcome measures between baseline and 8-week follow-up survey between intervention and control arms using all participants who completed both surveys. Cohen’s d effect size was calculated by taking the difference between group mean change scores and dividing by the pooled standard deviation. All analyses were intent-to-treat. As a pilot study, this randomized clinical trial was not adequately powered to detect statistically significant differences between groups. As such, standardized effect sizes were calculated to demonstrate effects and trends. Effect sizes of approximately 0.2, 0.5,

and 0.8 are generally considered small, medium, and large effects, respectively.

As a supplementary analysis, we conducted dose-response per-protocol analyses, repeating the analysis but stratifying intervention participants by level of adherence to the mindfulness intervention protocol (percent of days during intervention period used Headspace: <50% and $\geq 50\%$) and comparing with the control participants.

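### Efficacy is summarised by uncorrected Cohen's d, which is biased slightly away from zero in small samples; Hedges' g would remove the bias at almost no cost

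*Combined protocol and SAP*

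**What the plan says.** All of this is in the Data Analyses section of the combined protocol and SAP. For preliminary efficacy, "we performed repeated measures analysis of variance tests comparing change in outcome measures between baseline and 8-week follow-up survey", between arms, among people with both surveys. Next to this the plan defines a standardised effect: the Cohen's d "effect size was calculated by taking the difference between group mean change scores and dividing by the pooled standard deviation". No small-sample correction is mentioned there or elsewhere.

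The plan gives d particular weight. It says that "this randomized clinical trial was not adequately powered to detect statistically significant differences between groups" and continues: "As such, standardized effect sizes were calculated to demonstrate effects and trends". The values are read against conventional benchmarks ("Effect sizes of approximately 0.2, 0.5" and 0.8).

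The formula is used on several subsets. "Data from patient participants and caregiver participants were analyzed separately", and a supplementary analysis repeats the comparison after "stratifying intervention participants by level of adherence to the mindfulness intervention protocol", with each stratum (below 50% of days, or 50% and above) set against the controls. No sample size is given for patients, caregivers, arms or strata.

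**The concern.** The pooled SD in the denominator is itself an estimate. With few degrees of freedom its reciprocal is too large on average, so the ratio overstates the magnitude of a real standardised effect. The smaller the comparison, the larger the overstatement. The plan turns to d because the trial is a small pilot, which is the setting where the correction has most to do.

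Two things are at stake. First, the pilot's effect sizes would be slightly too far from zero on average, and these are the values a reader would take from it. Second, the inflation differs between analyses: a stratum comparison uses only part of the intervention arm, so its d is inflated a little more than the whole-arm d in the same population. The supplementary analysis is described as a dose-response one, so the two sets of values are likely to be read together.

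**Working it through.** **Inputs.** From Data Analyses: the formula for d, the absence of a correction, the separate patient and caregiver analyses, and the two strata each compared with controls. From the Randomization paragraph: two arms in balanced blocks, taken here as about 1:1. The documents state no sample size, SD, power or dropout figure, so there is no figure of the plan's own to reproduce, and **every group size below is an assumption**.

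**Formulas.** For normal change scores with equal variance, an SD pooled over the two arms and df = n1 + n2 - 2:

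- E[d] = δ / J(df), where J(df) = Γ(df/2) / [√(df/2) · Γ((df-1)/2)], which is below 1
- J(df) ≈ 1 - 3/(4·df - 1)
- overstatement = 1/J - 1
- SE(d) ≈ √[1/n1 + 1/n2 + d²/(2(n1 + n2))]

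Example, 10 per arm: df = 18; approximate J = 1 - 3/71 = 0.9577 (exact 0.9576); overstatement 4.4%. A true 0.50 averages 0.50/0.9576 = 0.522. SE = √(0.1 + 0.1 + 0.25/40) = 0.454, so the bias of 0.022 is about 5% of one SE.

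| Assumed completers | df | J | Overstatement | Mean d if δ = 0.50 | SE | Bias/SE |
|---|---|---|---|---|---|---|
| 5 vs 5 | 8 | 0.903 | 10.8% | 0.554 | 0.64 | 8% |
| 10 vs 10 | 18 | 0.958 | 4.4% | 0.522 | 0.45 | 5% |
| 15 vs 15 | 28 | 0.973 | 2.8% | 0.514 | 0.37 | 4% |
| 20 vs 20 | 38 | 0.980 | 2.0% | 0.510 | 0.32 | 3% |
| 40 vs 40 | 78 | 0.990 | 1.0% | 0.505 | 0.23 | 2% |

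**Simulation** (200,000 replicates, true effect 0.50). Mean d was 0.522, 0.510 and 0.504 at 10, 20 and 40 per arm; the corrected value averaged 0.499 to 0.500. With no true effect, mean d was zero to within 0.001.

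**Whole arm against stratum.** If both strata contain participants, each has fewer intervention participants than the arm, so df falls whatever the sizes are. Suppose the arm splits in half and the full control arm is kept:

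| Whole arm | Stratum | Overstatement, whole arm → stratum |
|---|---|---|
| 10 vs 10 | 5 vs 10 | 4.42% → 6.27% |
| 20 vs 20 | 10 vs 20 | 2.03% → 2.78% |
| 40 vs 40 | 20 vs 40 | 0.97% → 1.32% |

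In the middle row the difference on a true 0.50 is 0.514 - 0.510 = 0.004.

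**The case against.** The best case against raising this is that it is immaterial. From 10 per arm upward the bias is under 5% of d and no more than about 5% of one SE; at 10 per arm the 95% half-width is about 0.89 (1.96 × 0.454). The benchmarks are themselves approximate, so a label could change only for a value already at a boundary. The plan names its statistic and formula, and anyone with the group sizes can convert d to g. The analysis of variance also contributes to the efficacy results and is unaffected. All of this stands. It makes the point minor but does not remove the bias.

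It is also fair to say that larger matters sit in the same sentences. No confidence interval for d is described, and the plan does not say whether the pooled SD is of change scores or raw scores. With equal SDs at both times, change-score d divided by raw-score d is 1/√(2(1-ρ)): 0.85 at an assumed correlation of 0.3 and 1.58 at 0.8. The correction resolves neither matter. Equally, neither makes it unnecessary: under normality the same J applies to a raw-score SD pooled over the two arms at one time point.

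A reader might infer more than the documents support:

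- **That caregivers are the worst affected group.** No numbers are given, and the Recruitment paragraph lets caregivers join without an enrolled patient. A smaller caregiver sample is plausible but is an assumption.
- **That a patient-versus-caregiver comparison is distorted.** The plan analyses the two populations separately and specifies no such contrast.
- **That the bias flatters the intervention.** It magnifies harmful and beneficial effects alike and creates none where the true effect is zero.
- **That every reported d is too large.** The bias is a property of the average over repeated samples, not of any single value.

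**Conclusion.** The point holds as a minor one. The specified d is uncorrected and is biased away from zero, on average and in either direction, whenever a true effect exists. Its size in this trial cannot be established from the documents; at assumed sizes of 40, 20 and 10 per arm it is about 1%, 2% and 4.4%. The one ordering that follows from the design alone is that, within a population, each non-empty adherence stratum set against all controls is inflated more than the whole-arm comparison, by about one percentage point or less for the sizes shown from 20 per arm upward.

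These results assume normal change scores, equal variances and an SD pooled across arms. No conclusion that an effect exists or is absent depends on the bias.

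**What to change.** Report Hedges' g in place of d for patients, caregivers and each adherence stratum:

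g = d × [1 - 3/(4·df - 1)], with df = n1 + n2 - 2, where n1 and n2 are the completers in that comparison and the SD is pooled across arms.

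Name g in the methods and in the table headings, and give n1 and n2 beside each value.

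The cost is one multiplication per effect size and one sentence of text, with no new data. Values move slightly toward zero: a d of 0.50 becomes 0.495 at 40 per arm (0.50 × 0.9904), 0.490 at 20 (0.50 × 0.9801) and 0.479 at 10 (0.50 × 0.9577). Because the multiplier is below 1, the sampling variance also falls slightly. The repeated measures analysis of variance is untouched.

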Participant-Reported Measures. We collected outcome data using self-administered online surveys using DatStat software (DatStat Ilume, version 6.1.18.19, Seattle, WA) at the time of consent (baseline survey) and immediately post-intervention (8-week survey) using validated questionnaires as follows.

Distress. The NCCN Distress Thermometer was used to assess current distress level. Respondents were asked to rate their level of distress during the past week by choosing a number, with 0 indicating no distress and 10 extreme distress.

Anxiety and depression. We used the 14-item Hospital Anxiety and Depression Scale (HADS) to assess anxiety and depression. Higher scores indicate greater anxiety and depression.

Pain. The PROMIS Pain Intensity numeric rating scale asks participants to rate average pain level in the past 7 days on a scale of 0 (“no pain”) to 10 (“worst imaginable pain”). The 8-item PROMIS Pain Interference scale assesses extent to which pain interfered with functional activities during the past 7 days. Higher scores indicate more interference due to pain.

Sleep quality. The 8-item PROMIS Sleep Disturbance scale assesses sleep disturbance during the past 7 days. A higher summary score indicates worse sleep disturbance.

Quality of life. We used the 27-item Functional Assessment of Cancer Therapy General Scale (FACT-G) to assess QoL in patients. FACT-G asks respondents to rate their QoL in 4 domains (physical, social/family, emotional, and functional well-being). Caregiver QoL was determined using the Caregiver Quality of Life Index–Cancer (CQOLC) scale. The CQOLC gauges the daily and overall impact caregiving has on respondents’ QoL. Higher scores indicate better QoL on both scales.

Fatigue. The 9-item Brief Fatigue Inventory assesses the severity and impact of fatigue on various aspects of life in the past 24 hours. Higher scores indicate greater fatigue.

Posttraumatic growth. The 21-item Posttraumatic Growth Inventory (PTGI) assesses 5 factors of posttraumatic growth, positive change experienced because of a traumatic event or crisis—relating to others, new possibilities, personal strength, spiritual change, and appreciation of life. Respondents are asked to rate to what extent they have seen the listed changes as a result as a crisis in their lives. We modified the wording to ask about changes as a result of their (patients) or their loved one’s (caregivers) cancer diagnosis. Higher scores indicate greater post-traumatic growth.

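### Low power is the stated reason for using Cohen's d to demonstrate effects, but d rests on the same difference in mean change as the underpowered test, and no interval is described

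*Combined protocol and SAP*

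**What the plan says.** All of this is in the combined protocol and SAP.

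- **Timing of outcomes** (Participant-Reported Measures): surveys were completed "at the time of consent (baseline survey) and immediately post-intervention (8-week survey"), so each outcome has two measurements.
- **Test** (Data Analyses): "To obtain preliminary efficacy results, we performed repeated measures analysis of variance tests comparing change in outcome measures" between arms, in participants who completed both surveys.
- **Effect size** (Data Analyses): Cohen's d is obtained by "taking the difference between group mean change scores and dividing by the pooled standard deviation". The text does not say whether this SD is of change scores or of raw scores.
- **Reason for the effect size** (Data Analyses): the trial "was not adequately powered to detect statistically significant differences between groups". The next sentence makes the effect sizes a consequence of this: "standardized effect sizes were calculated to demonstrate effects and trends".
- **Benchmarks** (Data Analyses): values of about 0.2, 0.5 and 0.8 "are generally considered small, medium, and large effects, respectively".
- **Scope** (Data Analyses): "Data from patient participants and caregiver participants were analyzed separately". A supplementary analysis compares subgroups with the control arm, "repeating the analysis but stratifying intervention participants by level of adherence to the mindfulness intervention protocol".

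No confidence interval, standard error or other measure of precision is described, either for d or for the difference in mean change.

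**The concern.** The argument runs from low power to effect sizes to demonstration. The second step does not follow. Low power means that the difference in mean change is estimated too imprecisely to be told apart from zero. Dividing that difference by an SD changes its units and does not make it more precise. The plan thus gives d the task that the test cannot perform, and leaves out the interval that would show how imprecise d is.

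At stake is how the preliminary efficacy results are read. A d near 0.2 would carry the label of a small effect in a text that says effect sizes demonstrate effects. At pilot sizes its interval would include no effect and also an effect in the opposite direction. The outcomes are numerous (distress, anxiety and depression, two pain scales, sleep, quality of life, fatigue, posttraumatic growth and mindfulness). They are analysed separately for patients and caregivers, and again within adherence strata, where the groups are smaller.

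**Working it through.** **Inputs.** From the documents: two arms with balanced allocation (taken as 1:1), two time points, the definition of d, and the three benchmarks. The documents give no sample size, alpha, SD or power figure, so there is no figure of the plan's own to reproduce. Assumed: two-sided 5% level, equal arms of n, and d on the pooled SD of change scores (the natural reading; the alternative is in step 5).

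**1. How d relates to the test.** With two time points, the group-by-time F equals the square of the two-sample t on change scores, and t = d / √(1/n₁ + 1/n₂). Hence

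F = d² / (1/n₁ + 1/n₂).

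One simulated data set with arms of 25 and 22 gave F = t² = 2.187 and d = 0.432. By the formula, 0.432² / (1/25 + 1/22) = 0.1866 / 0.0855 = 2.18, which agrees up to rounding of d. In 2,000 simulated data sets with unequal arms of 8 to 59, the largest relative discrepancy was 4.5 × 10⁻⁹.

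**2. Arm size at which the interval around an observed d excludes zero.** With equal arms the condition is d√(n/2) ≥ t₀.₉₇₅ on 2n − 2 degrees of freedom. No value for the trial's own arm size is needed.

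| Observed d | Smallest n per arm | d√(n/2) | Critical t |
|---|---|---|---|
| 0.2 | 194 | 1.970 | 1.966 |
| 0.5 | 32 | 2.000 | 1.999 |
| 0.8 | 14 | 2.117 | 2.056 |

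At n = 193 and d = 0.2, the statistic is 1.965 against 1.966 and just fails.

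**3. Illustration at assumed arm sizes.** The interval inverts the noncentral t distribution. The chance rates are P(t on 2n − 2 df ≥ c√(n/2)) with no true effect, for one outcome, in the direction favouring the intervention. The half-width near d = 0 is t₀.₉₇₅√(2/n).

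| Assumed n per arm | 95% CI for observed d = 0.2 | ANOVA p | Chance of d ≥ 0.2 | Chance of d ≥ 0.5 | Half-width near 0 |
|---|---|---|---|---|---|
| 15 | -0.52 to 0.92 | 0.59 | 29% | 9.1% | 0.75 |
| 30 | -0.31 to 0.71 | 0.44 | 22% | 2.9% | 0.52 |
| 50 | -0.19 to 0.59 | 0.32 | 16% | 0.7% | 0.40 |
| 75 | -0.12 to 0.52 | 0.22 | 11% | 0.1% | 0.32 |

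For example, at n = 50 and c = 0.2, the statistic is 0.2 × √25 = 1.00 on 98 df, with upper tail 0.160. At 40 per arm the chance of d ≥ 0.5 is 1.4%. These rates are not the probability that an observed d of 0.2 is due to chance.

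**4. Adherence strata.** Suppose a stratum holds about half the intervention arm and is compared with all controls. The half-width is t₀.₉₇₅√(1/m + 1/n): 0.64 for 15 v 30, 0.49 for 25 v 50 and 0.39 for 38 v 75. This is before any bias from self-selected adherence.

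**5. If the SD is of raw scores.** With equal variances at both times and baseline-to-8-week correlation r, SD of change = SD of raw scores × √(2(1 − r)). The exact identity is lost and the thresholds move, but the numerator of d and its sampling error do not change.

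| Assumed r | n per arm, d = 0.2 | n per arm, d = 0.5 | Chance of d ≥ 0.2 at n = 50 |
|---|---|---|---|
| 0.3 | 271 | 45 | 20.0% |
| 0.5 | 194 | 32 | 16.0% |
| 0.7 | 117 | 20 | 10.0% |
| 0.8 | 79 | 14 | 5.9% |

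**The case against.** The strongest reply is that this turns on one verb. 'Demonstrate', paired with 'trends', can mean no more than illustrate. The efficacy results are called preliminary and the low power is stated openly. No success threshold or go/no-go rule rests on d, and the benchmarks are offered only as convention. Retention and adherence come first among the outcomes. The ANOVA is specified alongside d, and by the identity above a reader with d and the numbers analysed could recover the p-value and the interval. The document is a short methods text without results, so its silence on intervals does not show that none were reported. The thresholds also depend on a change-score SD that the text does not specify.

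Much of this stands. Reporting effect sizes in a pilot is sound practice, and the chance rates treat descriptive labels as cut-offs, which the plan does not do. The absence of an interval is an absence from the described analysis only. The thresholds are conditional, as step 5 shows.

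What does not stand is the rationale. Even on the softer reading, the admission of low power serves as the reason for turning to d and is not carried over as a limit on d. A p-value does not show the range of effects compatible with the data. Recovering the interval by hand requires the numbers analysed and knowledge of which SD was used, and the text does not name the SD.

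**Conclusion.** The concern holds. Low power is the stated reason for using d to demonstrate effects, no interval is described, and d rests on the same difference in mean change as the ANOVA. That conclusion does not depend on the arm sizes.

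The size does depend on assumptions. With equal arms and a change-score SD, small, medium and large observed values of d are separated from zero at the 95% level only from 194, 32 and 14 per arm. With a raw-score SD and r from 0.3 to 0.8, the threshold for d = 0.2 ranges from 271 down to 79. At every arm size illustrated, 15 to 75, the interval around an observed d of 0.2 covers zero and negative values. The problem is mainly with small values: chance values of 0.5 or more favouring the intervention are uncommon from about 40 per arm. It should be corrected, but it does not invalidate the point estimates.

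**What to change.** State that the effect sizes are calculated to estimate the size of between-arm differences, with their uncertainty, in place of demonstrating effects and trends. Report each between-arm difference in change in scale units and as d, each with a 95% confidence interval and the number analysed, for patients, for caregivers and for each adherence stratum. Name the SD used as the denominator of d.

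The cost is one change of wording and a little more analysis of data already collected. The point estimates stay the same. The intervals may show the preliminary efficacy results to be imprecise.

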Participants were asked to complete Headspace sessions on a daily basis during the 8-week intervention. They were encouraged to first complete the 30-day Foundation Course, which teaches users the basics of mindfulness meditation, then the cancer pack, which was designed specifically for individuals affected by cancer. They also had the option to choose other 10- to 30-day courses that are more condition- or situation-specific, such as "Anxiety," "Stress," "Acceptance," "Relationships," or "Sleep," or single meditation sessions. All Headspace courses teach mindfulness using various basic techniques, including breathing exercises, body scan (to mindfully pay attention to different parts of one's body—one of the most basic exercises in the MBSR program), noting (being aware of any emotions that may be arising at the moment), and visualization (visualizing images such as sun shining on the entire body). The length of the sessions can be set from 10 to 20 minutes. The length was initially set to 10 minutes for all participants. In addition to the daily, progressive audio instruction, there are short (1-2 minutes) lecture videos every several days designed to increase the understanding of mindfulness and to encourage its integration into daily life. Headspace can be set up to send reminders using push notifications, and study staff made phone calls if an intervention participant completed fewer than 3 Headspace sessions in a week.

Wait-list Control Arm. Participants randomized to the waitlist control arm received usual care and were asked not to start any stress reduction programs during the study period. On completion of the 8-week survey, the control participants were provided with a year's subscription to Headspace and instructions on downloading the app.

Outcome Measures

Retention. The retention rate was measured as the proportion of enrolled participants who completed the 8-week survey (the primary outcome time point).

Adherence. The Headspace program automatically collects adherence data, including date, time, length, and name of each session to which participants listened, identified by a study ID. Headspace transferred these adherence data to the researchers monthly during the study. Using these data, we calculated the proportion of days during the 8-week intervention period that each participant used the program for any amount of time.

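### The supplementary dose-response analysis describes only stratum-versus-control comparisons; no high-versus-low contrast, trend or confidence interval is described

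*Combined protocol and SAP*

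**What the plan says.** In the combined protocol and SAP, the last paragraph on quantitative methods under Data Analyses begins "As a supplementary analysis, we conducted dose-response per-protocol analyses". The method is given as "repeating the analysis but stratifying intervention participants by level of adherence to the mindfulness intervention protocol", with the cut stated as "percent of days during intervention period used Headspace: <50% and" its complement, "and comparing with the control participants".

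The analysis being repeated is the main efficacy analysis: "repeated measures analysis of variance tests comparing change in outcome measures between baseline and 8-week follow-up survey between intervention and control arms", in participants who completed both surveys. The accompanying effect size is defined as follows: "Cohen’s d effect size was calculated by taking the difference between group mean change scores and dividing by the pooled standard deviation". No interval is described for it.

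The same section states that "this randomized clinical trial was not adequately powered to detect statistically significant differences between groups" and that standardised effect sizes are therefore the means of showing effects and trends, read against benchmarks of 0.2, 0.5 and 0.8. Patients and caregivers are analysed separately.

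Under Outcome Measures, Adherence, the plan says that "we calculated the proportion of days during the 8-week intervention period that each participant used the program for any amount of time". A continuous adherence measure therefore exists for each intervention participant.

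**The concern.** A dose-response statement is about the difference between doses. Comparing low users with control and high users with control gives two effect sizes, but neither the difference between them nor its uncertainty. A larger d in one stratum does not show that the strata differ. Nor does a significant test in one and a non-significant test in the other.

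The layout invites that reading. The analysis is labelled dose-response, the results are to be read as effect sizes and trends, and the effect sizes have no intervals. A reader who sees a small d for under 50% use and a medium d for higher use is likely to conclude that more use brings more benefit, and nothing in the output would show how easily chance produces that pattern.

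This is separate from self-selection into adherence levels: it would apply even if the level of use had been assigned at random.

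**Working it through.** **The plan's own figure.** There is none to reproduce. The documents give no sample size, stratum size, SD or power value.

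**Inputs.**
- From Data Analyses: two strata cut at 50% of days; comparator control; d = difference in mean change divided by the pooled SD; benchmarks 0.2, 0.5 and 0.8.
- Assumed: m participants in each stratum (equal strata), change-score SD = 1, control group of 2m, two-sided 5% level.
- Chosen for illustration: a gap of 0.3, the distance between the small (0.2) and medium (0.5) benchmarks. The plan sets no such threshold.

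**Step 1: the gap.** With a common SD s,

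d(high) − d(low) = (mean_high − mean_control)/s − (mean_low − mean_control)/s = (mean_high − mean_low)/s.

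The control mean cancels, so SE(gap) = √(1/m + 1/m) = √(2/m).

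**Step 2: chance of a misleading gap.** With the same true effect in both strata, P(gap ≥ 0.3 in the expected direction) = 1 − Φ(0.3/SE).

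| m per stratum (assumed) | SE = √(2/m) | 95% half-width = 1.96 × SE | 0.3/SE | P(gap ≥ 0.3) |
|---|---|---|---|---|
| 10 | 0.447 | 0.88 | 0.671 | 0.251 |
| 15 | 0.365 | 0.72 | 0.822 | 0.206 |
| 20 | 0.316 | 0.62 | 0.949 | 0.171 |

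A simulation that estimates the pooled SDs as the plan would (100,000 runs per scenario, common true effect of 0 or 0.5) gives 0.26, 0.21 and 0.18.

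**Step 3: sensitivity to the assumed sizes.** In the same simulation the probability is about 0.32 at m = 5 and 0.07 at m = 50. An uneven split of 10 and 20 gives SE = √(1/10 + 1/20) = 0.387 and a probability of about 0.22.

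**Step 4: reading significance instead.** With a common true effect of 0.5 in both strata, and so no dose effect, exactly one stratum is significant against control in 29%, 35% and 38% of simulated trials at m = 10, 15 and 20.

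**Step 5: what a direct contrast could show.** Power to detect a true high-minus-low gap of 0.5 SD is 20%, 28% and 35% at m = 10, 15 and 20. For 80% power, about 63 per stratum are needed for a gap of 0.5 SD and 175 for 0.3 SD. The contrast would therefore mainly display the uncertainty.

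**The case against.** The strongest reply is that this is a supplementary analysis in a pilot that disclaims power and calls its efficacy results preliminary, and that the plan contains no dose-response conclusion and no rule for drawing one. That is fair. It limits the consequence to how this one analysis is interpreted. It does not remove the problem, because the label names a quantity that the described method does not estimate.

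Four stronger readings are tempting, and the documents do not support them.

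- **That the strata are never compared with each other.** The text is silent on such a comparison; it does not exclude one. A single three-group repeated measures ANOVA would also fit the wording. Its omnibus test would still not be a dose contrast, so the accurate statement is that none is described.
- **That the shared control group makes the gap misleading.** A chance poor control result moves both effect sizes together and cancels from their difference (Step 1). It is not a reason to distrust the gap.
- **That each stratum is about half an arm.** No stratum sizes are given. The equal split is an assumption made here.
- **That an interval excluding zero would establish a dose-response.** High and low users select themselves after randomisation, so the contrast is not a randomised comparison, whatever its interval. Such a gate would also act as a significance test in a trial that disclaims power. Counting anxiety and depression separately, about ten outcomes are listed. If they were independent, the chance of at least one false pass in the expected direction would be 1 − 0.975^10, about 22%, in each population analysed.

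**Conclusion.** The point stands as a gap between label and method. The analysis is called dose-response, but the only comparisons described are with control, and no high-versus-low contrast, trend or confidence interval is given. On the assumed equal strata of 10 to 20, chance alone produces a gap of 0.3 or more in the expected direction in roughly one trial in four to one in six, for each outcome. The size depends on the assumed stratum numbers and on the 0.3 illustration; the missing contrast does not. The randomised between-arm analysis, retention and adherence rates are not affected. This should be changed, but it does not threaten the trial's main results.

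**What to change.** For each outcome, and separately for patients and caregivers, fit one model with three groups (control, under 50%, 50% or more) and report the high-minus-low difference in mean change with its 95% CI. Alternatively, report the slope of change on the continuous adherence proportion within the intervention arm, with its CI; this avoids the 50% cut.

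Describe either result as an exploratory association whatever the interval shows. Do not use dose-response as a conclusion drawn from the two stratum-versus-control effect sizes. If those are still shown, give them intervals and call them descriptive.

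The cost is one extra estimate per outcome from data already held. The downside is that the intervals will be wide (about ±0.6 to ±0.9 SD at the assumed sizes) and will seldom support a gradient. The change addresses only the chance-gap problem; confounding by who chooses to use the programme remains.
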